1. Protocol

Protocol Title

Aligning the Visit Priorities of Complex Patients and their Primary Care Providers – PCORI 1403-11992

Principal Investigator

[name] MPH

Version Date

7/12/18

Form Author

[name]

Objectives

For **Aim 1** our study objectives were to obtain patient and provider views of their priorities for primary care visits and how to format a PC tablet based tool designed to help complex patients determine their top priorities for their upcoming primary care appointment. In Aim 1, we conducted an iterative series of separate one-on-one interviews with complex patients and their PCPs to characterize the process of prioritization, understand how patients and their providers differ in setting priorities, and create a process for how these differences can be negotiated during time-limited primary care visits.

In **Aim 2** we developed a simple web-based application that can be loaded onto a Tablet PC to be used in the waiting room prior to the visit. This tool was designed to guide patients to define and discuss their top priorities for the visit. IRB approval was not required for this aim as it did not involve human subjects.

In **Aim 3**, we examined the impact of this tool on both patient-centered and clinical care outcomes. We compared complex patients in intervention vs. control arms to test the following hypotheses:

H1: The intervention increases patient satisfaction, autonomy, perceived patient-centeredness, and quality of communication (patient-centered outcomes).

H2: The intervention reduces quality care gaps (clinical outcome).

H3: The intervention improves collaboration (patient/provider outcomes).

2. Background

a. Scientific Background

Patients are Increasingly Complex: The aging of the US population coupled with better disease prevention and treatment efficacy means that more patients are living with multiple comorbidities that require complicated medical regimens.^{1,2} By 2020 there will be an estimated 130 million Americans with one or more chronic conditions.^{3,4} Patients with multiple chronic conditions have more outpatient visits per year, are often prescribed up to 20 medications, generate more health care costs, have more adverse events, and have lower health-related quality of life.⁵ For this proposal, we define “**complex patients**” as patients with two or more chronic conditions who are not receiving the full potential benefit of health

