The Solution to Competing Demands is Effective Prioritization: While team care and non-visit based interactions are increasingly common for managing complex patients, the primary care visit remains a critical opportunity for patients and providers to directly engage in shared decision making. For patients with multiple concurrent conditions, however, a critical and often underappreciated first step in this process is the decision about which issues to discuss first. Prior research using videotaped encounters has shown that the first item addressed during the primary care visit receives the bulk of the attention (5 minutes vs. 1.1 minutes for the next 5 of six total topics addressed during the typical 15 minute visit).¹⁷ Neglecting this critical aspect of patient-provider communication and collaboration may have important negative consequences for complex patients with multiple health-related (and non-health-related) concerns. Indeed, other visit content analyses have found that more complex patients are less likely to have medication changes compared to less complex patients,¹⁸ and the likelihood of preventive screening declines with each additional concern brought up by patients.¹⁹

While the basic concept of encouraging patients to prepare for their physician appointments and to ask questions during the visit is not new,²⁰ there is a paucity of data demonstrating the clinical impact and the optimal implementation of this approach for complex patients.^{21,22} Truly patient-centered care requires that care interactions include consideration of patient priorities. For example, pain symptoms in older patients have been associated with a 3-fold greater difficulty taking medications prescribed for other chronic conditions, and thus addressing a patient's pain would likely lead to more effective medication management for these other conditions.²³ Research by our group and others has demonstrated that it is not simply the number of concurrent diagnoses, but the influence of behavioral, emotional, and social factors that create substantial barriers to effective clinical care.^{24,25}

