Intervention patients are provided the Visit Planner on a tablet tool in the waiting room. The tool starts off with a video that explained the purpose of the application and educated patients about the importance of bringing up their concerns early rather than later in the visit. Then, the tool prompts them to choose their top 1 or 2 concerns for the visit from 6 categories (New Problem, Medicines, Need something from the doctor, Old Problem, Stress at home or at work, A personal concern or other). Within each category, patients have the option of choosing 3-4 sub-categories and of inputting additional comments in a free-text field. After identifying their top visit priorities, patients are then prompted to identify how they would use their time during or after the visit to stay involved with their care (e.g., Take notes during the visit, Ask my doctor questions during the visit, Review with a friend or loved one, Check online patient portal after the visit). All patient responses are subsequently printed out as a Visit Planner Summary for the patient to bring into their visit.

Control

Control patients are also met in the waiting room before eligible visits. Control patients are given a 1-page healthy lifestyle education handout.

Patients in both study arms otherwise receive usual care throughout the clinical trial period.

4. Study Population

a. Number of Subjects

Aim 3 clinical trial = 750 patients (modified)

b. Inclusion and Exclusion Criteria

PCP Eligibility: Providers are eligible for inclusion if they have at least 5 potentially study-eligible patients within their patient panel and plan to remain at their current practice for the following year.

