- a. If you will obtain surrogate consent, describe detailed research plan to the surrogate, including present and future decisions to be made. A documented assessment of decisional capacity as part of the procedures for obtaining surrogate consent should be included.

N/A

Other Populations Targeted for Recruitment

N/A

d. Setting

The clinical trial was conducted within KPNC primary care practices located at Oakland and San Francisco – Mission Bay. Study procedures were conducted by research personnel.

e. Recruitment Methods

On 1/22/16, the IRB approved the “Aligning Patient and Providers” clinical trial. Intervention arm patients have the opportunity to use the Align Waiting Room Tool (an iPad based application that helps them prepare for their visit) while control patients receive a KP-designed handout on healthy lifestyle advice.

We have the following research protocol for our clinical trial:

- 1) As with our procedure for our similar ongoing clinical trial (CN-13-1579 – Pre-Visit Prioritization for Complex Patients with Diabetes), [name] contacts Primary Care Practice Leaders (via e-mail or in-person) to request permission to present the “Aligning Patient and Providers” clinical trial at a weekly practice meeting. At this meeting, [name] explains the purpose for his visit, describes the study, and identifies providers willing to participate. With help from research staff, [name] then obtains written informed consent from willing physicians. Consenting physicians also review a list of their own potentially eligible patients to approve contacts and complete the 5-item baseline questionnaire at this time. This entire process takes 20-30 minutes.
- 2) PCP-approved patients are then sent a letter explaining the study. The letter includes a phone number and e-mail address for patients who wish to participate or opt out of the study. After 1 week, we contact patients who have not yet responded and – using our phone script – invite patients to participate in our study.

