Our primary patient-reported outcomes regarding their care experiences are obtained during post-visit telephone calls using questions drawn from validated survey instruments. Surveys are conducted within 1 week of the eligible primary care visit. We measure outcomes in the domains of patient satisfaction, autonomy, perceived involvement in care, and satisfaction with care.²⁹⁻³⁴ Modeled on the structure of these validated items, we also add several study-specific questions to obtain more detailed information about bringing up top concerns at the beginning of the visit, taking notes and asking questions during the visit, and following up post-visit with friends

and loved ones. Finally, we examine responses to a 5-item PCP survey administered at baseline during study enrollment.

Statistical Methods

We examine baseline characteristics of patients and providers by randomization status using chi-square, t-test, and non-parametric tests as appropriate. For our clinical trial outcomes, we construct generalized linear mixed models (SAS Proc GLIMMIX) with the dichotomized response as a dependent variable (with a logit link), treatment/control arm as a fixed effect and PCP as a random effect to adjust for clustering of patients within PCP. For secondary survey outcomes, the patient reports are dichotomized and analyzed in the same type of mixed models. We also conduct a priori analyses of English vs. Spanish-speaking patients in sub-analyses to determine any differential effects by language. We use SAS version 9.3, SAS Institute, Cary NC.

b. Sharing of Results with Subjects

Results will not be directly shared with patients.

c. Data and/or Specimen Banking

NA

6. Privacy, Confidentiality and Data Security

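### Does H3 (collaboration) need a plan change because its only provider measure is a baseline PCP survey?

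*Combined protocol and SAP*

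**What the plan says.** The Objectives state three hypotheses for the Aim 3 comparison of arms. The one at issue reads "H3: The intervention improves collaboration (patient/provider outcomes"). H2 concerns quality care gaps. The first reads "H1: The intervention increases patient satisfaction, autonomy, perceived patient-centeredness, and quality of communication (patient-centered outcomes").

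Section 5a, Study outcomes, describes three kinds of measure:

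- care gaps at baseline and 6 months;
- post-visit telephone reports from patients in four domains (patient satisfaction, autonomy, perceived involvement in care, satisfaction with care), plus study-specific questions about visit behaviour;
- the provider survey: "Finally, we examine responses to a 5-item PCP survey administered at baseline during study enrollment".

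Section 4e (Recruitment Methods) fixes when the provider survey happens. In the consent session PCPs review their patient lists and "complete the 5-item baseline questionnaire at this time". The next step is that "PCP-approved patients are then sent a letter explaining the study".

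Under Statistical Methods, provider characteristics are compared by arm at baseline, and the survey-outcome models are for patient reports. Section 5 also lists provider surveys as a data source, without saying when they are given.

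**The concern.** H3 is the only hypothesis whose label mentions providers, and the only provider data described are collected before the intervention reaches any of that PCP's study patients. The survey is placed under Study outcomes, so a reader could take it for the provider half of H3. Read that way, the trial would be claiming an effect on a quantity measured before exposure.

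The patient half is also unassigned. No measure in section 5a is called collaboration, so a reader cannot tell in advance which result would support or refute H3. At stake would be a hypothesis with no test, or one whose outcome is chosen after the data are seen.

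**Working it through.** No formula applies, and the plan gives no figure to reproduce. The check sets the hypotheses against the measures, their timing and their models.

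**1. Hypotheses against section 5a**

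| Hypothesis | Measure that fits by content | Respondent and timing | Model described |
|---|---|---|---|
| H1, patient-centred outcomes | Post-visit patient domains | Patient, after the visit | Mixed model, PCP random effect |
| H2, care gaps | Care-gap measures | Record, baseline and 6 months | Mixed model, PCP random effect |
| H3, collaboration | None assigned; perceived involvement in care is a plausible candidate | Patient, after the visit | Mixed model, if that domain is used |
| None stated | 5-item PCP survey | PCP, at enrolment | None for effect; could enter the baseline comparison |

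Section 5a does not cite H1, H2 or H3 by number for any measure; the first two are matched only by content. Two H1 constructs (perceived patient-centredness and quality of communication) are likewise not repeated by name there. Since the survey items are not in the documents, a tally of recurring labels would not show which constructs are measured, and I do not rely on one.

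**2. Timing of the PCP survey**

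The order in section 4e is PCP consent and survey, then the patient letter, the enrolment call, and the visit with the tool or handout. The text does not say whether the survey falls before or after randomization. Either way it precedes exposure of that PCP's patients, so it can describe providers, check balance or serve as a covariate. It cannot carry an intervention effect. Counts from the text: PCP surveys described for Aim 3, 1 at baseline and 0 after exposure; models for PCP responses, 0.

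**3. Does the plan misuse the survey?**

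The sentence says only that responses are examined, and gives the time point. Nothing ties it to H3 or to a comparison of effect. An analyst following Statistical Methods would have no instruction to treat it as a treatment outcome, and the baseline comparison of providers is its natural place.

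**4. What H3 could mean**

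- *Collaboration as patients report it.* The Scientific Background treats collaboration as a property of the pair: "Neglecting this critical aspect of patient-provider communication and collaboration" is described as possibly harmful to complex patients. On this reading the post-visit patient survey can serve, and perceived involvement in care is already collected and modelled. Only the label is missing.
- *Collaboration as providers report it.* On this reading nothing described can test it. The last visit was on 6/30/17, follow-up ended on 12/31/2017 and the version date is 7/12/18. An edit at that point cannot add a post-visit PCP survey that was not done.

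**5. What an edit would alter**

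An edit could move one sentence to the baseline characteristics, name a patient item for H3, or narrow H3's wording. None of these adds data, changes a model or alters an estimate for care gaps or patient reports.

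**The case for a change.** The strongest case for a change is that Aim 3 says it tests H3, and a hypothesis with no assigned outcome leaves the choice open until results are known. One patient item could be used to support both H1 and H3. The study-specific questions are a tempting choice, yet they overlap with what the tool teaches: its video "educated patients about the importance of bringing up their concerns early rather than later in the visit", and its planning options include "Take notes during the visit, Ask my doctor questions during the visit, Review with a friend or loved one". A difference on those items might show uptake of the tool rather than better collaboration. The version date also falls after follow-up ended, so an outcome named in this version is not thereby prespecified.

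Part of this stands. H3 has no named outcome, respondent or time point, and the baseline PCP survey cannot supply one. The rest concerns uses that the plan does not propose. The study-specific questions are introduced to give finer detail on the visit, not as measures of collaboration, and raising concerns early lies on the intervention's intended path, so whether it counts as uptake or collaboration is a matter of judgement. Double counting is possible but nothing in the text calls for it. The late version date also weakens the case for an edit, because an outcome first named then would be post hoc whatever the text said.

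The untimed mention of provider surveys in section 5 does not show that a later PCP survey took place. It does mean that one should not assert that none did.

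**Conclusion.** The observation is accurate, but no change to the plan follows. It is a minor gap in outcome specification: H3 has 0 assigned outcomes, and there are 0 post-exposure PCP measures and 0 models for PCP responses. The statement that H3 cannot be tested holds only if H3 includes provider-reported collaboration, which the documents leave open. On the patient-reported reading a suitable domain is already collected and modelled. On the provider-reported reading no wording would help.

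The care-gap analysis (H2) and the patient-reported models are unaffected, and no rule in the plan would lead an analyst to present the baseline survey as an intervention effect. For the reader of the results, the PCP survey describes providers, and a result offered in support of H3 is exploratory unless an earlier dated plan names its outcome.

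This rests on two assumptions: that the 5-item survey at enrolment is the only PCP survey in Aim 3, as it is the only one described, and that perceived involvement in care is close enough to collaboration to serve as a patient-side measure. The second cannot be verified, because the survey items are not in the documents. If a post-visit PCP survey was in fact done, H3 would be better supplied than it appears here.

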not meeting one or more evidence-based primary care management outcomes related to preventive screening [e.g. cancer screening], disease management [i.e. risk factor testing or control], or medication taking [evidence of non-adherence based on pharmacy dispensing or self-report]). In these Step 1 interviews, we focus on understanding whether and how patients prepare for upcoming visits and how they conceptualize the relative importance of different health issues. For each participant, we also elicit a specific list of their current health care priorities that they want to discuss with their physician. With each patient's prior consent, in Step 2 we interview each participant's physician. In the Step 2 interviews we elicit the physician's priorities for the patient, compare the physician and patient listed priorities, and investigate how each physician would seek to balance any differences between the two sets of priorities. Finally, in Step 3 we close the loop by returning to the patient. In the Step 3 interviews, we present patients with physician priorities and investigate how the patient perceives any differences between his/her priorities and PCPs.

Aim 2 is the IT development of the tablet application and does not involve human subjects.

Aim 3 Clinical Trial

We conducted a 2-arm parallel group clinical trial with random, concealed allocation at the level of PCP. Both PCPs and patients provided informed written consent. Patients, providers, and waiting room research assistants cannot be blinded to randomization status because treatment patients are given the Visit Planner tool in the waiting room while control patients are not. However, collection of post-visit survey data and assembly of analytic datasets is masked to randomization status. For **Aim 3**, we enroll PCPs and their patients from KPNC primary care practices in Oakland and San Francisco. PCPs are recruited via their weekly practice meetings and through individual in-person contacts.

Intervention

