Patient Eligibility: We use the KPNC electronic clinical data repository to identify a broad spectrum of potentially eligible patients within each participating PCP's patient panel. Patient eligibility is defined as having **2 or more chronic conditions** (defined using our validated clinical data algorithms for the following common chronic conditions: type 2 diabetes, hypertension, cardiovascular disease, dyslipidemia, chronic obstructive pulmonary disease/asthma, depression, renal insufficiency, cancer, and symptomatic arthritis) and **1 or more Quantitative Clinical Care gaps** defined using KPNC-implemented quality metric algorithms (e.g. preventive cancer screening for breast, cervical, and/or colorectal cancer screening among screen-eligible patients; and to chronic disease management including annual HbA1c testing and **result < 8.0%** for patients with diabetes; annual blood pressure measurement and systolic blood pressure (SBP) < 140 mg Hg for patients with diabetes, hypertension, or cardiovascular disease (CVD); annual cholesterol measurement and LDL < 100 mg/dL for patients with diabetes or CVD). We exclude patients with psychosis or dementia or other deficits that significantly impair communication or use of computers. Screening is conducted via electronic record review and patient phone calls. We retain information from decliners so that subjects are not re-contacted after declining.

c. Vulnerable Populations

We do not make any special effort to include or exclude vulnerable populations, however our study only includes adult members with at least two complex conditions who can participate in an English or Spanish language interview. Each subject, including those in a vulnerable population listed above who may be randomly selected into our study sample, have the opportunity to decline participation and avoid further contact by study staff by returning the mailed reply postcard or by phoning the study coordinator. Given the very low-risk nature of study participation, i.e. survey completion on a PC tablet or interview participation, no additional safeguards, beyond standard confidentiality safeguards, are employed. TPMG physicians are assured that no individual identifiable responses gathered during interviews will be shared with others outside of the study team.

Decisionally Impaired Adults

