1. Securing storage of physical data (e.g., papers) in locked files, and securing storage of digital data (computer files, digital audio) in password-protected files on password protected computers.
2. Making data that may contain identifying features accessible only to members of the research team working under the direction of the investigators during the duration of the project.
3. Use of a study ID on all audio files and transcripts. The transcriptionist do not transcribe any identifying information. Study staff review hard copy transcripts and remove any remaining identifying information (such as names, place names, etc.). All audio files are destroyed after transcription.
4. Ensuring that no data are collected or maintained by investigators which participants do not want to have preserved.
5. Ensuring no participant can be identified in any presentations or publications about this study.
6. All study staff rated current in HIPAA and IRB training.

All drugs and devices used in the research and the purpose of their use, and their regulatory approval status. NA
The source records that will be used to collect data about subjects. Data are collected from the medical record and via patient and provider surveys.

What data will be collected including long-term follow-up. Long-term follow-up is based on data from the medical record collected as part of routine care.

The duration of an individual subject's participation in the study. Physicians were recruited at monthly physician meetings where the study was presented. The first eligible patient visit occurred on 3/31/2016 while the last visit occurred on 6/30/17.

The duration anticipated to enroll all study subjects. Enrollment of physicians began 2/2016 and was completed by 2/2017. Follow-up was assessed through 12/31/2017— 6 months after the final visit. We chose a 6-month follow-up period to balance factors of providing sufficient time for the intervention to make an impact while also reducing loss to follow-up.

a. Data Analysis

Study outcomes

Our primary clinical outcome is the closing of quality care gaps within 6 months of study visits. Individual care gaps are measured at baseline and 6-month follow-up as a total count of any care gap at both time periods. Change in aggregated care gaps from baseline to follow-up is also assessed in four ways: closure of all baseline gaps, closure of any baseline gaps, opening of new care gaps, and presence of no gaps at the end of the study.

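### The care-gap models omit the baseline gap count already collected; adding it to three of them is a cheap improvement with a small, assumption-dependent power gain

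*Combined protocol and SAP*

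**What the plan says.** Section 5a, Statistical Methods, gives one logit mixed model for the trial outcomes, with "treatment/control arm as a fixed effect and PCP as a random effect to adjust for clustering of patients within PCP". No other term is listed. The only use made of baseline data is descriptive: "We examine baseline characteristics of patients and providers by randomization status".

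Under Study outcomes in the same section, "Individual care gaps are measured at baseline and 6-month follow-up as a total count of any care gap at both time periods". The outcomes built on these counts are "closure of all baseline gaps, closure of any baseline gaps, opening of new care gaps, and presence of no gaps", the last of them judged when follow-up closes.

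Section 4b requires "1 or more Quantitative Clinical Care gaps" at entry, so counts start at one and may go higher. Section 3 (Aim 3 Clinical Trial) describes "random, concealed allocation at the level of PCP" and no stratification or other balancing. Section 4a gives "Aim 3 clinical trial = 750 patients".

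**The concern.** A patient with three gaps must close three to count as all-closed; a patient with one must close one. The baseline count therefore enters the definition of the outcome, yet the model ignores it. Because PCPs are allocated and no balancing is described, mean counts can differ between arms by chance. The unadjusted odds ratios then shift with a difference that the trial has measured but does not use.

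At stake are some power and the ease of interpreting the result if the arms differ at baseline. Validity is not at stake. No claim is made for the opening of new gaps, which is not tied to the baseline count in this way.

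**Working it through.** **Inputs.** From the document: 750 patients, allocation by PCP, the two model terms, a baseline count of at least one. The 750 cannot be reproduced, because no alpha, power, effect size, event rate or intracluster correlation is given. Everything else below is assumed: one to three gaps per patient, equal arms (375 each), the closure rates, and a new-gap risk of 0.15.

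**1. Direction.** Let q_k be the closure probability per gap for a patient with k gaps. If gaps close independently, P(all closed) = q_k^k and P(any closed) = 1 − (1 − q_k)^k. Whatever the dependence between gaps, P(all) cannot exceed the per-gap rate. With q_1 = 0.40:
- More gaps make all-closed likelier only if q_2 exceeds √0.40 = 0.632, or q_3 exceeds 0.40^(1/3) = 0.737.
- More gaps make any-closed less likely if q_2 is below 1 − √0.60 = 0.225, or q_3 is below 1 − 0.60^(1/3) = 0.157.

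The document does not settle which pattern holds.

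**2. Shift with no treatment effect.** Suppose one arm has 55/30/15% of patients with 1/2/3 gaps (mean 1.60) and the other 45/35/20% (mean 1.75). For flat closure of 0.40, all-closed is 0.55×0.40 + 0.30×0.16 + 0.15×0.064 = 0.2776 against 0.45×0.40 + 0.35×0.16 + 0.20×0.064 = 0.2488. No-gaps is all-closed × 0.85. Differences in percentage points:

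| q_1/q_2/q_3 | All closed | No gaps at end | Any closed |
|---|---|---|---|
| 0.40/0.40/0.40 | −2.9 | −2.4 | +3.1 |
| 0.40/0.30/0.25 | −3.5 | −3.0 | +1.4 |
| 0.40/0.22/0.15 | −3.7 | −3.2 | −0.1 |
| 0.40/0.50/0.60 | −1.7 | −1.4 | +4.4 |

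Last row: all-closed 0.3274 against 0.3107; any-closed 0.5854 against 0.6297.

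**3. How large an imbalance to expect.** The 55/30/15 mix has variance 0.54. Without clustering, the SD of the difference in means is √(2×0.54/375) = 0.054. With some clustering of counts by PCP (latent correlation 0.05), 6 to 25 patients per PCP, and this mix or 35/35/30%, simulation gave 0.058 to 0.086. The 0.15 used above is thus 1.7 to 2.6 SD (0.15/0.086 to 0.15/0.058). Scaling the first three rows to 1 SD gives about −1.1 to −2.1 points (all), −0.9 to −1.8 (no gaps) and −0.1 to +1.8 (any).

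**4. Validity and dependence on imbalance.** The planned model was simulated with 750 patients as 30×25, 50×15 or 125×6, both mixes and the first three closure patterns: 36 settings of 1,000 replicates.
- Type I error was 3.2–6.3% without the count and 3.4–6.3% with it.
- The correlation between imbalance and the estimated log odds ratio, unadjusted, was −0.25 to −0.56 (all), −0.23 to −0.52 (no gaps) and −0.15 to +0.35 (any). Adjusted, it was within 0.12 of zero.

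**5. Power and standard error.**
- Same 36-setting simulation, per-gap odds ratio 1.5: +4.4 to +10.6 points (all), +1.9 to +7.4 (no gaps), −0.1 to +6.0 (any). Every pattern here is flat or falling.
- A separate mixed-model simulation (60 PCPs, other gap mixes, 400 replicates): 1 to 5 points (all), 2 to 3 (no gaps), 3 to 9 (any). In its middle case for all-closed, the log odds ratio went from 0.400 to 0.428 and its standard error from 0.186 to 0.193. The ratio rises from 2.15 to 2.22, and power from 56% to 61%.
- Rising closure (50×15, cluster-robust logistic, 2,000 replicates): with 0.40/0.50/0.60, all-closed power went from 59.1% to 59.6% and no-gaps from 51.8% to 51.6%. With 0.40/0.55/0.65, all-closed went from 59.3% to 59.2%.
- A narrower mix (80/15/5%, flat 0.40): all-closed went from 54.7% to 56.4%.

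So the standard error does not shrink. Power rises, where it does, because the conditional log odds ratio lies further from zero.

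**The case against.** The strongest reply is that the planned model is valid, its interval already allows for chance imbalance, and the benefit may be nil. Rising closure is plausible: the metrics in section 4b pair annual tests with control thresholds, so one round of overdue tests could close several gaps together. The gain for all-closed and no-gaps then disappears. All effect sizes are assumed, and the 0.15 imbalance is larger than a typical one. All of this stands, and it is why the point is an improvement and not an error.

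It could also be argued that any-closed should be left out because its direction is open. That does not follow: where closure rises with the count, so that all-closed gains nothing, any-closed is most strongly tied to the count (the last row of the table).

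A reader might infer three stronger things that the documents do not support:
- That the unadjusted comparison is biased or has inflated type I error. Allocation is random, and the simulations show neither model misbehaving.
- That adjustment narrows the interval for the odds ratio. On the logit scale it does not.
- That a gain of 4 to 10 points can be counted on for all-closed. That range comes only from flat or falling closure, and the document gives no closure rates.

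On timing, this version is dated 7/12/18 and section 5 puts the end of follow-up at 12/31/2017. That does not show that outcomes had been seen when the model was written, but it limits what a change can now do.

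**Conclusion.** The point holds as a cheap improvement. The model leaves out a covariate that is already collected and tied by definition to three outcomes. Including it removes nearly all of the estimates' dependence on imbalance in gap counts. It adds about zero to several points of power: about zero for all-closed and no-gaps if closure rises with the count, and about zero for any-closed if closure falls steeply.

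The qualitative result rests on the outcome definitions and on PCP-level allocation. The sizes rest on assumed closure rates, gap mixes, PCP numbers, correlations and a per-gap odds ratio of 1.5. Confidence in the sizes is moderate at best.

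**What to change.** In the models for all-closed, any-closed and no-gaps-at-end, add the baseline gap count as a linear fixed effect. Fit it separately per outcome, because its sign can differ, and keep the PCP random effect. One linear term suffices: under the assumed patterns, a term per count category usually added 0.02 or less to R². Take the count from the electronic record at or before the patient's first study visit, so that the visit cannot alter it; the source exists ("Screening is conducted via electronic record review and patient phone calls"). Leave the new-gaps model unchanged.

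Report the unadjusted model alongside and label the adjusted odds ratio as conditional on baseline count. If a precision gain on a marginal scale is wanted, add a standardised risk difference from the adjusted model.

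State whether outcomes had been seen before this version. If they had, the written model stays as the main analysis and the adjusted one is a labelled sensitivity analysis.

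The cost is one term per model from data already held, a move from a marginal toward a conditional odds ratio that must be labelled, and possibly no gain for some outcomes.
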